5.5.3.3. Assessment of Toxicity During Phase 2 Dose Expansion

Sequential boundaries will be used to monitor the DLT rate during Phase 2 dose expansion (Ivanova 2005). The accrual will be halted if excessive numbers of DLTs (boundary) as defined in Section 5.5.3.2 are seen per arm, and the SMC will have the option of either discontinuing accrual in that arm or reducing the RP2D to reduce the level of toxicity. The boundaries at which accrual is halted or the RP2D is reduced are listed in Table 6. This is a Pocock-type stopping boundary that yields the probability of crossing the boundary at most 5% when the rate of dose-limiting toxicity is equal to the acceptable rate of 30%.

Table 6: Early Stopping Boundaries for Toxicity

Number of Patients	1	2	3	4	5	6	7	8	9	10	11	12	13	14	15
Boundary	-	-	-	4	5	5	6	6	7	7	8	8	9	9	9
Number of Patients	16	17	18	19	20	21	22	23	24	25	26	27	28	29	30
Boundary	10	10	11	11	12	12	12	13	13	14	14	14	15	15	15

An early safety analysis of the first 6 patients randomized to receive nanatinostat and valganciclovir with pembrolizumab will be performed, and a more conservative early stopping boundary than is shown in Table 6 above will be applied if appropriate. If at least two of these patients experience DLTs during their first 2 cycles (7 weeks) of treatment, then patient accrual will be halted, and the SMC will have the option of either discontinuing accrual in that arm or reducing the RP2D to reduce the level of toxicity.

5.6. Dose Modification Guidelines for Study Treatment-Related Toxicities

Nanatinostat and Valganciclovir

For patients who do not tolerate the protocol-specified dosing schedule or develop toxicities, dose adjustments of nanatinostat and valganciclovir are permitted. Dose adjustments, except for valganciclovir adjustments based on renal function (Section 5.6.2), must be approved by the Medical Monitor or Sponsor prior to implementing. These changes must be accurately recorded in the eCRFs.

Given the expectation that both study drugs are required for activity, both agents will be held and restarted in parallel. Dose modification guidelines in case of study treatment-related toxicity for nanatinostat, valganciclovir, and pembrolizumab are presented in Table 7.

Unless otherwise indicated in Table 7, any AE that requires a dose hold should resolve to Grade 1 or baseline generally within 14 days before resuming treatment at the current or a reduced dose.

The management of patients requiring more than 2 dose reductions should be discussed with the Sponsor's Medical Monitor.

For patients in Phase 2 treated with nanatinostat and valganciclovir in combination with pembrolizumab, if pembrolizumab treatment is discontinued, nanatinostat and valganciclovir dosing may continue. If nanatinostat or valganciclovir are discontinued, the Sponsor's Medical Monitor should be consulted about pembrolizumab treatment.

Pembrolizumab

Dose reduction of pembrolizumab will not be required in this study. For the management of specific immune-mediated adverse reactions, see Table 8. Otherwise, withhold pembrolizumab for severe (Grade 3) immune-mediated adverse reactions and permanently discontinue pembrolizumab for those that are life-threatening (Grade 4), recurrent Grade 3 that require systemic immunosuppressive treatment, or if not able to reduce corticosteroid dosing to 10 mg per day or less of prednisone or an equivalent within 12 weeks of initiating steroids.

If a patient requires a dose interruption of >6 weeks of pembrolizumab from the intended day of the next scheduled dose, pembrolizumab should be discontinued.

Exceptions following a discussion between the Sponsor's Medical Monitor and the Investigator may be possible. Reasons for a potential exception include, but are not limited to, the following:

- 1. Dosing delays to allow for prolonged steroid tapers to manage drug-related AEs.
- 2. Dosing delays lasting >6 weeks from the previous dose that occur for non-drug-related reasons (eg, surgery) may be allowed.

Patients with permanent discontinuation of pembrolizumab due to adverse reactions may continue treatment with nanatinostat and valganciclovir provided that they could still potentially benefit from the treatment (in the opinion of the Investigator) until disease progression, occurrence of intolerable toxicity, death, Investigator's decision, or voluntary withdrawal of the patient from the study.

The Investigator must first discuss any decision about permanent drug discontinuation in advance with the Sponsor's Medical Monitor. All doses of study treatment and all dose interruptions or modifications must be accurately recorded in the eCRFs.

For additional details on pembrolizumab dosing, refer to the current prescribing information (Keytruda [pembrolizumab] Prescribing Information, 2023).

Table 7: Dose Modification Guidelines for Study Treatment-Related Toxicity

NCI CTCAE v5.0	Recommended Dose Modifications for Nanatinostat and	Recommended Dose Modifications
Toxicity Grade	Valganciclovir	for Pembrolizumab
Grade 4 neutropenia (ANC <0.5 × 10 ⁹ /L)	 Interrupt nanatinostat/valganciclovir dosing. Resume nanatinostat/valganciclovir at the same doses when ANC ≥1.0 × 10⁹/L. If the grade 4 neutropenia lasts more than 7 days or recurs, then decrease valganciclovir dose by 50% daily. For dose levels 6 and 7: decrease twice daily valganciclovir dosing to once daily dosing (take with nanatinostat). If the decreased dose is tolerated for ≥4 weeks, then resume previous daily valganciclovir dose. If Grade 4 neutropenia occurs again following a valganciclovir dose reduction, then interrupt nanatinostat/valganciclovir dosing and discuss with the medical monitor. 	Withhold until resolution to Grade 0 or 1.
	6. Use of growth factors (G-CSF, GM-CSF) is permitted per the ASCO 2015 clinical practice guidelines (Smith 2015).	
Grade 3 neutropenia (ANC 0.5 – <1.0 × 10 ⁹ /L)	 If persistent (>7 days) then interrupt nanatinostat/valganciclovir dosing. Resume nanatinostat/valganciclovir at the same doses when ANC ≥1.0 × 10⁹/L. If recurs and persists >7 days, then consider reducing daily valganciclovir dose by 50%. For dose levels 6 and 7: decrease twice daily valganciclovir dosing to once daily dosing (take with nanatinostat). If persists, then decrease nanatinostat daily dose to the next lowest nanatinostat dose level. Use of growth factors (G-CSF, GM-CSF) are permitted per the ASCO 2015 clinical practice guidelines (Smith 2015). 	Maintain dose and schedule.

NCI CTCAE v5.0 Toxicity Grade	Recommended Dose Modifications for Nanatinostat and Valganciclovir	Recommended Dose Modifications for Pembrolizumab
Grade 4 thrombocytopenia (Platelet count <25 × 10 ⁹ /L)	 Interrupt nanatinostat/valganciclovir dosing. If thrombocytopenia resolves to ≤Grade 2 (>50 × 10⁹/L), then restart both drugs. If recurs, then decrease daily valganciclovir dose by 50%. For dose levels 6 and 7: decrease twice daily valganciclovir dosing to once daily dosing (take with nanatinostat). If the decreased dose is tolerated for ≥4 weeks, then resume previous daily valganciclovir dose. If Grade 4 thrombocytopenia occurs again following a valganciclovir dose reduction, then interrupt nanatinostat/valganciclovir dosing and discuss with the medical monitor. 	If ongoing at time of next scheduled pembrolizumab dose, omit scheduled dose. If asymptomatic, resolved to ≤Grade 2 within ≤7 days and prior to scheduled dose, proceed with pembrolizumab dose.
Grade 3 anemia (Hemoglobin <8.0 g/dL)	 Continue nanatinostat and decrease valganciclovir dose as follows: from 900 mg twice daily to 900 mg daily; from 900 mg daily to 450 mg daily; from 450 mg daily to 450 mg every 2 days; from 450 mg every 2 days to 450 mg twice weekly. If anemia persists, then decrease nanatinostat daily dose to the next lowest nanatinostat dose level. If anemia resolves to ≤Grade 2 (≥8.0 g/dL), after (1), then increase valganciclovir dose. Increase nanatinostat dose if it was decreased per (2). If anemia recurs, then decrease valganciclovir dose as outlined in (1) and maintain at the lower dose. Transfusion is recommended in patients with a hemoglobin level <7-8 g/d L per institutional guidelines, and/or with symptomatic anemia 	Maintain dose and schedule.
Grade 4 anemia	 Hold both study drugs. Transfuse. Once anemia resolves to ≤Grade 2 (≥8.0 g/dL), resume nanatinostat at the planned dose and valganciclovir at a lower dose as follows: Decrease 900 mg twice daily to 900 mg daily; decrease 900 mg daily to 450 mg daily; decrease 450 mg daily to 450 mg every 2 days; decrease 450 mg every 2 days to 450 mg twice weekly) If anemia persists, then decrease nanatinostat daily dose to the next lowest nanatinostat dose level. If recurs, interrupt both drugs and discuss with the study's Medical Monitor. 	Maintain dose and schedule.
Febrile neutropenia (ANC <1.0 × 10 ⁹ /L, with a single temperature of ≥38.3°C or a sustained temperature of ≥38°C for more than 1 hour)	 Interrupt nanatinostat/valganciclovir dosing. Resume nanatinostat/valganciclovir at the same doses when ANC ≥1.0 × 10⁹/L. Use of growth factors (G-CSF, GM-CSF) are permitted per the ASCO 2015 clinical practice guidelines (Smith 2015). 	Withhold until resolution to Grade 0 or 1.
QTc prolongation	 For QTc interval >480 msec and <500 msec: Check magnesium and potassium levels and correct any abnormalities. If possible, stop any medications that may prolong the QTc interval. Decrease nanatinostat to the next lowest nanatinostat dose level. Resume nanatinostat/valganciclovir at the initial dose in the next cycle provided that the QTc interval improves to ≤470 msec at the start of that cycle. Otherwise continue nanatinostat at the next lowest nanatinostat dose level. 	Maintain dose and schedule.

NCI CTCAE v5.0	Recommended Dose Modifications for Nanatinostat and	Recommended Dose Modifications
Toxicity Grade	Valganciclovir	for Pembrolizumab
	 For QTc interval >500 msec: Check magnesium and potassium levels and correct any abnormalities. Interrupt nanatinostat/valganciclovir dosing and stop any medications that may prolong the QTc interval. If the QTc interval improves to ≤470 msec just prior to the start of the next cycle, resume nanatinostat/valganciclovir at the initial dose. If no other cause of QTc prolongation is identified, decrease dose of nanatinostat to the next lowest nanatinostat dose level. Otherwise continue to hold nanatinostat/valganciclovir for as long as necessary. 	
Other study drug- related Grade 3/4 non-hematologic toxicity or Grade 3/4 clinically significant laboratory abnormalities	 Grade 4 non-hematologic AE: Discontinue nanatinostat/valganciclovir dosing. Following resolution of the toxicity to ≤Grade 1 or to the patient's baseline value, if the Investigator considers it to be in the patient's best interest to resume therapy, this may be permitted at a lower dose level following discussion with Sponsor's Medical Monitor. Grade 3 non-hematologic AE: Resume nanatinostat/valganciclovir at the same dose when toxicity resolves to ≤Grade 1. 	See Table 8.
Treatment-related Grade 5 toxicity	Pause further enrollment in the study pending a Safety Monitoring Committee assessment.	Pause further enrollment in the study pending a Safety Monitoring Committee assessment.

Dose levels for Phase 1b are defined in Table 4.

AE = adverse event; ANC = absolute neutrophil count; ASCO = American Society of Clinical Oncology; CTCAE = Common Terminology Criteria for Adverse Events; G-CSF = granulocyte-colony stimulating factor; GM-CSF = granulocyte macrophage-colony stimulating factor; NCI = National Cancer Institute; PO = orally; QD = once daily.

Table 8: Pembrolizumab Recommended Dose Modifications for Immune-Mediated Adverse Reactions

Adverse Reaction	Severity	Pembrolizumab Dose Modification
Pneumonitis	Grade 2	Withhold ¹
	Grades 3 or 4	Permanently discontinue
Colitis	Grades 2 or 3	Withhold ¹
	Grade 4	Permanently discontinue
Hepatitis with no tumor involvement of the liver	AST or ALT increases to >3 and up to 8 × ULN or total bilirubin increases to more than 1.5 and up to 3 × ULN	Withhold ¹
	AST or ALT increases to more than 8 × ULN or Total bilirubin increases to more than 3 × ULN	Permanently discontinue
Hepatitis with tumor involvement of the liver ²	Baseline AST or ALT is more than 1 and up to 3 × ULN and increases to more than 5 and up to 10 × ULN or Baseline AST or ALT is more than 3 and up to 5 × ULN and increases to more than 8 and up to 10 × ULN	Withhold ¹
	AST or ALT increases to more than 10 × ULN or Total bilirubin increases to more than 3 × ULN	Permanently discontinue

Adverse Reaction	Severity	Pembrolizumab Dose Modification
Endocrinopathies	Grades 3 or 4	Withhold until clinically stable or permanently discontinue depending on severity
Nephritis with renal dysfunction	Grade 2 or 3 increased creatinine	Withhold ¹ . Follow guidelines for valganciclovir dose reduction in Table 7. Resume in patients with complete or partial resolution (Grades 0 to 1) after valganciclovir dose adjustment and/or corticosteroid taper
	Grade 4 increased creatinine	Permanently discontinue
Exfoliative dermatologic conditions	Suspected SJS, TEN, or DRESS	Withhold ¹
	Confirmed SJS, TEN or DRESS	Permanently discontinue
Myocarditis	Grade 2, 3 or 4	Permanently discontinue
Neurological toxicities	Grade 2	Withhold ¹
	Grade 3 or 4	Permanently discontinue
Infusion-related reactions	Grades 1 or 2	Interrupt or slow the rate of infusion
	Grades 3 or 4	Permanently discontinue

Source: Keytruda [pembrolizumab] Prescribing Information, 2023

Patients should be monitored until resolution of the toxicity. During a dose interruption, study days and procedures will continue to accrue until the end of the current cycle (see Schedule of Events in Section 6). If the dose interruption extends beyond the end of the cycle, the subsequent Cycle Day 1 will not begin until dosing has resumed. If the dose is held for more than 14 days, the Investigator should consult with the Sponsor's Medical Monitor before dosing resumes.

If a patient has multiple dose interruptions for study drug toxicity or has had to interrupt for more than 14 days, a dose reduction may be considered. Re-escalation of study drug dose may only be performed after approval by the Sponsor's Medical Monitor.

5.6.1. Criteria for Suspension of Study Drug Treatment Due to Treatment-Related Toxicities

In the event of the following treatment-related toxicities, no additional patients should be enrolled until further review and assessment by the Safety Monitoring Committee:

- Death
- Grade 4 QTc prolongation (Torsade de Pointes)
- Occurring in ≥ 2 patients:
 - Grade 4 acute renal failure
 - Grade 4 multi-organ failure

¹Resume in patients with complete or partial resolution (Grades 0 to 1) after corticosteroid taper

²If AST and ALT are less than or equal to ULN at baseline, withhold or permanently discontinue KEYTRUDA based on recommendations for hepatitis with no liver involvement.

ALT = alanine aminotransferase; AST = aspartate aminotransferase; DRESS = Drug Rash with Eosinophilia and Systemic Symptoms; SJS = Stevens-Johnson Syndrome; TEN = toxic epidermal necrolysis; ULN = upper limit of normal

5.6.2. Dose Modifications for Patients with Renal Impairment

Patients who develop an elevated creatinine while on study should have their dose of valganciclovir adjusted per Table 9.

An estimated creatinine clearance in adults is calculated from serum creatinine by the following formulas:

For serum creatinine measured in mg/dL:

For males =
$$(140 - age [years]) \times (body weight [kg]) = XX mL/min$$

(72) × (serum creatinine [mg/dL])

For females =
$$(140 - age [years]) \times (body weight [kg]) = XX mL/min \times 0.85$$

(72) × (serum creatinine [mg/dL])

For serum creatinine measured in µmol/L:

For males =
$$(140 - age [years]) \times (body weight [kg]) \times 1.23 = XX mL/min$$

Serum creatinine (μ mol/L)

For females =
$$(140 - age [years]) \times (body weight [kg]) \times 1.23 = XX mL/min \times 0.85$$

Serum creatinine (µmol/L)

For patients already receiving a dose of valganciclovir lower than that recommended in Table 9, the Investigator should discuss the amount of dose reduction with the Sponsor's Medical Monitor.

Creatinine Clearance (mL/minute)	Valganciclovir Dose (daily)	Valganciclovir Dose (twice daily)
≥60	900 mg once daily	900 mg twice daily
40–59	450 mg once daily	450 mg twice daily
25–39	450 mg every 2 days	450 mg once daily
10–24	450 mg twice weekly	450 mg every 2 days
<10 (on hemodialysis)	Not recommended (discuss with Medical Monitor)	Not recommended (discuss with Medical Monitor)

 Table 9:
 Valganciclovir Dose Adjustments for Patients with Renal Impairment

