1.5.3.2. Valganciclovir Dose

For Phase 1b, valganciclovir will be administered at a dose of 900 mg once or twice daily with food. Once and twice daily dosing (900 mg/dose) are consistent with the labeled indication for the prevention and treatment, respectively, of CMV disease in kidney, heart, and kidney-pancreas transplant patients at high risk (Valcyte [valganciclovir] Prescribing Information, 2020). Once daily dosing was associated with a favorable safety and tolerability profile from the ongoing Phase 1b/2 VT3996-201 study in relapsed/refractory EBV⁺ lymphoma in combination with nanatinostat.

Twice daily dosing of valganciclovir for the first 21 days starting on Cycle 1 Day 1 with a subsequent reduction to 900 mg once daily will be introduced in dose level 6 (Table 4), in concert with a divided dose of nanatinostat starting at 10 mg twice daily. Although this dosing regimen was observed to have exceeded the MTD in the Phase 1b/2 VT3996-201 study in patients with relapsed/refractory lymphoma with 2 DLTs of grade 3 thrombocytopenia and 1 grade 4 neutropenia (Section 1.5.1.1), baseline hematology laboratory levels required for eligibility (hemoglobin ≥8.0 g/dL, absolute neutrophil count ≥1000/mm³, platelet count ≥50,000/mm³) were lower than those required for the current study (VT3996-301: Hemoglobin ≥9.0 g/dL, absolute neutrophil count ≥1500/mm³, platelet count ≥ 100,000/mm³). Therefore, the previous toxicity observed with these doses of nanatinostat and valganciclovir may not manifest in a different patient population with higher baseline hematology values required for eligibility. Twice daily dosing of 450 mg valganciclovir (900 mg/day; each dose 4 or 8 hours apart) together with twice daily dosing of nanatinostat (each dose 4 hours apart) will be explored in dose levels 6 and 7 and 8 − 13, to assess the impact of short-term "dose intensification" of valganciclovir upon safety, tolerability, and plasma EBV DNA levels.

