3. STUDY DESIGN

3.1. Description of Study Design

This is a Phase 1b/2, open-label, multicenter study designed to evaluate the safety and preliminary efficacy of oral nanatinostat and valganciclovir alone and in combination with IV pembrolizumab in patients with EBV⁺ RM-NPC (Figure 3).

Phase 1b:

A traditional 3+3 dose escalation design will be used to determine the RP2D of nanatinostat and valganciclovir; approximately 27 to 60 patients with RM-NPC will be enrolled; cohorts of 3 to 6 patients with RM-NPC will be enrolled sequentially at escalating nanatinostat doses starting with a 20 mg once daily dose on Days 1 to 4 per week (intermittent dosing) with valganciclovir 900 mg daily. Any patients in screening when the last patient is enrolled in a cohort may also be enrolled if eligible. Dose escalation will continue with i) a total daily nanatinostat dose of 30 and 40 mg daily administered as a single dose on Days 1 to 4 per week with valganciclovir 900 mg once daily, ii) as a divided nanatinostat dose twice daily on Days 1 to 4 per week with valganciclovir 900 mg once daily or valganciclovir 900 mg twice daily for 21 days followed by a subsequent dose reduction to 900 mg once daily, or iii) as a split daily dose of nanatinostat starting at 20 mg with valganciclovir 450 mg twice daily, 4 hours apart on Days 1 to 7 per week until the RP2D is determined. Because plasma EBV DNA levels correlate closely with the presence of disease and response to therapy in RM-NPC, these data will be considered together with safety data in the selection of the RP2D.

Phase 2:

Following dose escalation, Phase 2 will begin with a dose optimization cohort to assess the safety, tolerability, PK, pharmacodynamics, and antitumor activity of nanatinostat and valganciclovir and to confirm its RP2D in patients with RM-NPC.

Patients will be randomly assigned 1:1 to each treatment group (up to 20 patients in each treatment group for approximately 40 patients total) during the dose optimization cohort period. The starting doses of nanatinostat for the treatment groups will be the RP2D and another dose level below the RP2D (<RP2D) plus valganciclovir 450 mg twice daily, based on the Safety Monitoring Committee's (SMC's) review of the totality of the data from the previous Phase 1b cohorts.

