5.5. Dose Escalation Guidelines

5.5.1. Provisional Dose Levels

Table 4 describes the starting doses and the provisional dose levels of nanatinostat and valganciclovir (Phase 1b) and nanatinostat and valganciclovir with pembrolizumab (Phase 2 Dose Optimization and Phase 2 Expansion) to be evaluated. The actual dose levels will be determined based on available data following a discussion with Investigators during dose-escalation teleconferences. No intrapatient dose escalation will be permitted in the Phase 1b dose escalation.

Table 4: Phase 1b: Dose Levels – Nanatinostat and Valganciclovir

Dose Level	Nanatinostat Oral Dose on Days 1-4/Week	Valganciclovir Oral Dose Daily
-1	10 mg once daily	900 mg once daily
1	20 mg once daily	900 mg once daily
2	30 mg once daily	900 mg once daily
3	40 mg once daily	900 mg once daily
4	20 mg and 10 mg divided dose	900 mg once daily
5	20 mg twice daily	900 mg once daily
6	10 mg twice daily	900 mg twice daily × 21 days, then once daily
7	20 mg and 10 mg divided dose	900 mg twice daily × 21 days, then once daily
	Nanatinostat Oral Dose Twice Daily on Days 1-7/Week	Valganciclovir Oral Dose Twice Daily on Days 1-7/Week
8 ^a	20 mg and 10 mg divided dose	450 mg twice daily

9ª	20 mg and 20 mg divided dose 450 mg twice daily			
10 ^a	30 mg and 20 mg divided dose	450 mg twice daily		
11ª	30 mg and 30 mg divided dose	450 mg twice daily		
12ª	40 mg and 30 mg divided dose	450 mg twice daily		
13ª	40 mg and 40 mg divided dose	450 mg twice daily		

DLT = dose-limiting toxicity; RP2D = recommended Phase 2 dose

Guidelines for Dose Escalation 5.5.2.

During the DLT evaluation window of both phases of the study, patients who permanently discontinue study treatment prior to receiving 75% of the planned number of nanatinostat and valganciclovir doses or 2 pembrolizumab doses due to reasons other than study drug-related toxicity will not be considered evaluable for DLT and may be replaced.

Phase 1b

IND 154400

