The RP2D of nanatinostat in Phase 1b will be defined as the highest dose administered with standard daily doses of valganciclovir (900 mg once or 450 mg twice daily) for which <33% of patients experience a DLT (defined in Section 5.5.3) during the first treatment cycle (28 days) up to a maximum daily dose of 80 mg administered with food either as a single daily dose administered intermittently (Days 1 to 4 per week) or as a split dose twice daily administered continuously (Days 1 to 7 per week). In addition to toxicity, PK, antitumor activity, plus pharmacodynamic markers of disease response (plasma EBV DNA levels) will be considered in the final determination of the RP2D in consultation with the SMC. Dose escalation rules during Phase 1b are presented in Table 5.

Table 5: Phase 1b Dose Escalation Rules for Nanatinostat in Combination with Valganciclovir*

Dose level	Outcome	Action		
-1 Nanatinostat 10 mg daily,	If none of the first 3 patients experiences a DLT	Proceed to expansion cohorts.		
Days 1-4/wk	If 1 of 3 patients experiences a DLT	Enroll 3 more patients into dose level -1		
Valganciclovir 900 mg daily	If 1 of 6 patients experiences a DLT	Declare dose level -1 to be RP2D		
	If ≥2/6 patients experience a DLT	Convene safety review to discuss next steps.		
1 Starting dose	If none of the first 3 patients experiences a DLT	Proceed to dose level 2		
Nanatinostat 20 mg daily,	If 1 of 3 patients experiences a DLT	Enroll 3 more patients into dose level 1		
Days 1-4/wk	If 1 of 6 patients experiences a DLT	Proceed to dose level 2		
Valganciclovir 900 mg daily	If ≥2/6 patients experience a DLT	Decrease nanatinostat to dose level -1 and proceed.		
Nanatinostat 30 mg daily,	If none of the first 3 patients experiences a DLT	Proceed to dose level 3		
Days 1-4/wk	If 1 of 3 patients experiences a DLT	Enroll 3 more patients into dose level 2.		
Valganciclovir 900 mg daily	If 1 of 6 patients experiences a DLT	Proceed to dose level 3.		
	If ≥2/6 patients experience a DLT	Declare dose level 1 the RP2D.		

a: Dose levels 9, 11, and 13 are planned dose levels, while dose levels 8, 10, and 12 are planned provisional dose levels for stepping up or down based on the DLT profile to potentially better determine the RP2D. See Table 5 for further details.

Dose level	Outcome	Action			
3 Nanatinostat 40 mg daily,	If none of the first 3 patients experiences a DLT	Proceed to dose level 6.			

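### Table 9, the renal dosing rule for valganciclovir, has no column that starts from 450 mg twice daily (dose levels 8 to 13), so the dose cut depends on which column a site reads

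*Protocol*

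**What the plan says.** Protocol Section 5.6.2 gives the rule: "Patients who develop an elevated creatinine while on study should have their dose of valganciclovir adjusted per Table 9". Table 9 then lists doses by CrCl in two columns:

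- **Daily column:** 900 mg once daily at CrCl 60 or above, 450 mg once daily at 40 to 59, 450 mg every 2 days at 25 to 39, and 450 mg twice weekly at 10 to 24.
- **Twice-daily column:** 900 mg twice daily, 450 mg twice daily, 450 mg once daily and 450 mg every 2 days in the same bands.

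Below 10, both columns advise against the drug and refer to the Medical Monitor.

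Table 4 (Section 5.5.1) assigns levels 8 to 13 a dose of 450 mg under the header "Valganciclovir Oral Dose Twice Daily on Days 1-7/Week". Section 3.1 plans the same for Phase 2 dose optimization: "plus valganciclovir 450 mg twice daily". Section 1.5.3.2 gives the daily total: "Twice daily dosing of 450 mg valganciclovir (900 mg/day; each dose 4 or 8 hours apart".

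Section 5.6.2 has one fallback, a discussion with the Medical Monitor about the size of the reduction. It begins: "For patients already receiving a dose of valganciclovir lower than that recommended in Table 9". Section 5.6 exempts renal adjustments of valganciclovir from the prior approval that other dose changes need. SAP Section 3.3.1.2 repeats only that doses should be adjusted when creatinine rises.

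**The concern.** In Table 9, 450 mg twice daily appears once, as the step down from 900 mg twice daily at CrCl 40 to 59. It is never a starting dose. A site with a level 8 to 13 patient whose CrCl has fallen into that band can look under the twice-daily label, find the dose the patient already takes, and change nothing. Another site can reason from the 900 mg daily total, use the daily column, and halve the dose. Neither needs approval first.

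Valganciclovir is cleared by the kidney, and Section 1.4.2 notes that CrCl-based reductions are recommended. Section 1.6.2 names renal dysfunction as an overlapping toxicity of the two drugs. In the single-agent nanatinostat study, creatinine elevation was dose-limiting at 80 and 120 mg (Section 1.4.1.2), and level 13 reaches 80 mg a day. The other controls work on a different scale from Table 9, which acts as soon as CrCl is below 60. The dose-limiting toxicity criteria in Section 5.5.3.1 look to Grade 3 or higher laboratory abnormalities and holds of more than 7 days.

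**Working it through.** There is no statistical figure to reproduce. The check converts each Table 9 entry to an average daily dose and compares it with the assigned dose.

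**Inputs.** Table 9 entries (Section 5.6.2); assigned total of 900 mg/day for 450 mg twice daily (Section 1.5.3.2); entry CrCl of at least 60 mL/min (inclusion criterion 11f).

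**Conversion.** Every 2 days: 450 / 2 = 225 mg/day. Twice weekly: 450 × 2 / 7 = 129 mg/day.

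| CrCl (mL/min) | Daily column, mg/day (share of 900) | Twice-daily column, mg/day (share of 900) | Ratio |
|---|---|---|---|
| 60 or above | 900 (100%) | 1800 (200%) | 2.0 |
| 40 to 59 | 450 (50%) | 900 (100%) | 2.0 |
| 25 to 39 | 225 (25%) | 450 (50%) | 2.0 |
| 10 to 24 | 129 (14%) | 225 (25%) | 1.75 |

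**Each column against its own starting dose.** Daily column, from 900: cuts of 50%, 75% and 86%. Twice-daily column, from 1800: cuts of 50%, 75% and 87.5%. Both columns therefore halve the dose at CrCl 40 to 59. A patient on 450 mg twice daily read in the twice-daily column gets cuts of 0%, 50% and 75% instead. Halving 900 mg/day at 40 to 59 gives 450 mg/day, the daily column's entry.

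**How large a creatinine rise falls in the uncut band.** In the Cockcroft-Gault formula, at fixed age and weight, CrCl equals entry CrCl divided by the multiple of creatinine. The band runs from entry/60 to entry/40. The entry values of 80 and 100 are illustrative.

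- Entry 60: a rise of up to 60/40 = 1.5-fold.
- Entry 80: 80/60 = 1.33-fold to 80/40 = 2.0-fold.
- Entry 100: 100/60 = 1.67-fold to 100/40 = 2.5-fold.

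**Does the fallback clause apply?** It needs a current dose below the table's.

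- Against the twice-daily column at 40 to 59: 900 versus 900 mg/day, equal, so not triggered.
- Against that column's row for 60 or above: 900 versus 1800 mg/day, lower, so triggered.
- Against the daily column: 900 versus 900 at 60 or above, and higher than the table in every lower band, so not triggered.

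The answer depends on the row and column chosen, and the clause sets no dose in any case.

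**The case against.** The strongest reply is that the protocol, read as a whole, already points to the right column. The twice-daily column cannot have been written for this regimen, because its top row would double the assigned dose. Section 5.5.2 groups the two 900 mg/day regimens together as "standard daily doses of valganciclovir (900 mg once or 450 mg twice daily". Table 7 also cuts valganciclovir proportionally for toxicity, for example "then decrease valganciclovir dose by 50% daily" for prolonged or recurrent Grade 4 neutropenia. On this evidence the daily column is the better reading, and that stands. The 2.0-fold and 1.75-fold ratios measure the distance to the less plausible reading. A reader might infer from them that the protocol directs full dosing in renal impairment, or that a dosing error of that size is expected. The documents do not support either inference.

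The second reply is that the fallback clause can be read to speak of the dose held before any reduction. All patients enter at CrCl 60 or above, where the twice-daily column lists 900 mg twice daily. A level 8 to 13 patient is then below the table and goes to the Medical Monitor. This too is a fair reading, and it weakens the worry about sites acting alone. It does not close the gap: Section 5.6.2 does not say which row to compare with, the clause supplies no dose, and Section 5.6 lets sites make renal changes without prior approval.

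**Conclusion.** The point holds as a gap in the wording of a safety rule. Followed by its column label, Table 9 gives a level 8 to 13 patient no reduction at CrCl 40 to 59, where a patient on the same daily total taken once is halved. The better reading is available but unstated. The comparison takes average mg/day as the measure of dose.

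Severity is minor. SAP Section 4.8 records that enrollment ended after the final Phase 1b dose level and that Phase 2 did not open. The gap therefore matters only for level 8 to 13 patients still on treatment. The documents do not say how many were treated at these levels, how many remain, or how often renal events occurred in this trial.

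Three wider conclusions are tempting but unsupported:

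- **Much of the trial was exposed.** Counting dose levels says little about patients; Table 4 marks levels 8, 10 and 12 as provisional.
- **Tables 7 and 8 share a fault of the same weight.** The anemia steps in Table 7 also start from 900 mg regimens, but those changes need prior approval under Section 5.6. Table 8 sends creatinine cases to Table 7, but it concerns pembrolizumab, which was planned only for Phase 2. For Table 7's general Grade 3 row, Section 5.6.2 is already the specific rule on creatinine.
- **The results are affected.** No endpoint or planned analysis depends on the choice of column.

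**What to change.** Add a note to Table 9, subject to the sponsor's confirmation, that patients assigned 450 mg twice daily follow the daily column: 450 mg once daily at CrCl 40 to 59, 450 mg every 2 days at 25 to 39, and 450 mg twice weekly at 10 to 24.

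The note should also say which nanatinostat dose the remaining valganciclovir accompanies. Section 5.3.3 has patients at levels 8 to 13 take both drugs at breakfast and again at lunch, and the tablets are 450 mg, so halving means dropping one of the two doses. Keeping the breakfast dose is one option.

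The cost is wording only. Visits, samples and analyses stay as they are. With enrollment closed, a short letter to sites would cover anyone still on treatment.
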